5.2 Concomitant treatments

The steering committee (SC) does not recommend any standardized concomitant drug regimen. All additional treatments, aside from IVT and EVT, must adhere to "China Stroke Prevention and Treatment Guidelines (2021 Edition)" and "Chinese Guidelines for the Diagnosis and Treatment of Acute Ischemic Stroke 2018". According to both AHA/ASA and Chinese guidelines, antiplatelet or antithrombotic therapy is typically initiated 24 hours after EVT procedure. In case of stent placement, the patient should be administered clopidogrel (300mg) orally or tirofiban intravenously as soon as possible, followed by daily oral doses of clopidogrel (75mg) and aspirin (100mg) for 3 months.

5.3 Rescue medications

If deemed necessary by the interventionalist, the use of local (intra-arterial) rtPA is permitted for all patients enrolled in BEST-BAO. The SC recommends that rtPA be given as a 5 mg bolus at a 5–10 min interval (maximum 40 mg) and that vascular patency be checked after each bolus. Patients who have already received IVT should not be administered more than 30 mg of intra-arterial rtPA during the EVT.

For patients in the EVT alone group who do not achieve successful reperfusion (defined as eTICI 2b–3) within the 4.5-hour time window and do not achieve the maximum rtPA dose, they may subsequently receive IVT with rtPA at a dose of 0.9 mg/kg. The total amount of rtPA for IVT received before and after EVT should not exceed the dose specified in the guidelines.

6. Investigational products

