Intervention: In accordance with the 2019 AHA/ASA guidelines for early management of AIS and recommendations from the steering committee (SC): In EVT alone group, EVT will be performed as quickly as possible. In IVT followed by EVT group, patients will receive IVT with alteplase (0.9 mg/kg, maximum 90 mg in one hour) before EVT. Efforts will be made to minimize delays in EVT initiation due to IVT administration. EVT techniques include retrievable stent thrombectomy, thrombus aspiration, balloon angioplasty, stent implantation, or combinations thereof. The specific EVT approach will be at the discretion of the treatment team.

Primary endpoint: The primary endpoint of the study is the proportion of patients achieving mRS ≤ 2 at 90±14 days after stroke onset. The proportion of patients achieving the primary endpoint will be calculated for each group, along with the rate difference (RD) and its 95% confidence interval (CI). A log-binomial model with a log-link function will be used to adjust the rate difference for multiple covariates, including age, pre-stroke mRS, time from onset to randomization, stroke severity (baseline NIHSS), and collateral circulation status (baseline PC-CS). The adjusted RD and its 95% CI will be reported.

Secondary endpoints:

1. Proportions of patients with mRS = 0 or 1 and mRS = 0–3, and mRS score at 90±14 days after stroke onset.
2. NIHSS score at 18–24 hours after procedure, 24–74 hours after procedure, and 5–7 days after stroke onset and their changes from baseline.
3. Proportions of patients with a NIHSS score = 0 or 1, a NIHSS score = 0–2, a NIHSS score improvement ≥ 4 points, and a NIHSS score improvement ≥ 8 points. at 18–24 hours after procedure, 24–74 hours after procedure, and 5–7 days after stroke onset.
4. GCS score at 18–24 hours after procedure, 24–74 hours after procedure, and 5–7 days after stroke onset and their changes from baseline.
5. BI score and the proportion with BI = 95–100 at 30±7 and 90±14 days after stroke onset.
6. EQ-5D-5L score at 90±14 days after stroke onset.
7. eTICI score and successful reperfusion rates before and after EVT.
8. mAOL score and recanalization rates at 24–72 hours after procedure.
9. PC-ASPECTS score at 24–72 hours after procedure.
10. Lesion volume based on quantitative imaging detection at 24–72 hours after procedure and 5–7 days after stroke onset.

Safety endpoints:

1. All-cause mortality within 7, 30±7 and 90±14 days after stroke onset.

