The safety and efficacy of intravenous thrombolysis (IVT) with recombinant tissue plasminogen activator (rtPA) within 4.5 hours of symptom onset in AIS have been confirmed by numerous randomized controlled trials (RCTs). However, the heterogeneous presentation of posterior circulation AIS, the difficulty in clinical recognition compared to anterior circulation AIS, and the severe neurological deficits—especially the high mortality rate of AIS-BAO—pose various limitations on IVT. Endovascular treatment (EVT), including thrombectomy techniques, has substantially reduced the mortality and disability rates of patients with AIS-LVO. The key to treating AIS-BAO is recanalizing the acutely occluded basilar artery and rescuing the ischemic penumbra. Large RCTs have demonstrated that early EVT achieves better clinical outcomes in anterior circulation AIS-LVO patients eligible for mechanical thrombectomy compared to IVT alone^[2-8].

In recent years, while multiple large RCTs have confirmed the efficacy of EVT for anterior circulation AIS-LVO, evidence for EVT in posterior circulation AIS-LVO remains limited. The BEST trial enrolled AIS patients with vertebrobasilar artery occlusion within 8 hours of symptom onset to compare EVT plus standard medical treatment versus medical treatment alone. The results showed that the combination group achieved better outcomes at 90 days, with no significant difference in mortality or symptomatic intracranial hemorrhage (sICH) rates compared to the medical treatment-only group^[9]. Similarly, the BASICS trial, an international multicenter RCT, enrolled 300 AIS-BAO patients within 6 hours of symptom onset and compared EVT combined with standard medical treatment to standard medical treatment alone. This study found no significant differences between the two groups in good functional outcomes, sICH, or mortality^[10].

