ultra-early treatment for AIS within 6 hours of onset. However, the adoption of IVT for posterior circulation AIS is lower than that for anterior circulation AIS, potentially due to delays in diagnosis or missed diagnoses caused by the heterogeneity of AIS-BAO symptoms. Among AIS patients receiving IVT, posterior circulation strokes (PCS) account for about 5–19%. Studies comparing the efficacy and safety of IVT in PCS and anterior circulation strokes (ACS) have found that while the risk of hemorrhagic complications is halved for PCS, functional outcomes are similar, but mortality is higher^[13]. Clinically, IVT can be used as standalone therapy for AIS-BAO or as a prelude to EVT. Which approach better improves AIS-BAO outcomes remains uncertain.

To date, most studies on IVT with EVT have focused on anterior circulation AIS. Both IVT and EVT are time-dependent treatments for AIS, with EVT success hinging on prompt initiation and optimization of processes to reduce door-to-puncture time (DTP). The SKIP trial found no significant difference in the time from randomization to femoral artery puncture between only EVT and IVT with EVT^[14]. Similarly, the DEVT trial, conducted in China, also reported no difference in this time interval between the two groups^[15]. A meta-analysis of 38 observational studies including 11,798 AIS-LVO patients (56% of whom underwent IVT with EVT) also confirmed no significant difference in EVT procedural time between the two groups^[16]. For anterior circulation AIS-LVO, four recent RCTs showed mixed results. DIRECT-MT and DEVT demonstrated that only EVT was non-inferior to IVT with EVT in terms of good functional outcomes at 90 days, while SKIP and MR CLEAN-IV did not confirm non-inferiority. Thus, EVT alone requires further robust evidence^[17, 18]. Regarding safety, all four RCTs confirmed that IVT with EVT does not increase sICH rates^[14, 15, 17, 18]. Additionally, the aforementioned meta-analysis^[16] confirmed that IVT with EVT does not increase sICH risk. SKIP, DIRECT-MT, and DEVT further showed no significant difference in mortality between the two groups^[14, 15, 17]. However, the meta-analysis^[16] suggested that IVT with EVT significantly reduces 90-day mortality compared to only EVT. A real-world study^[19] also found that IVT with EVT was independently associated with lower 90-day mortality compared to only EVT.

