4.3 Inclusion criteria

Participants must meet all of the following criteria to be eligible for enrollment:

- (1) A clinical diagnosis of AIS.

(2) Caused by BAO confirmed by CTA, MRA, or DSA. (BAO is defined as the absence of visualization of the basilar artery on CTA, MRA or DSA. Bilateral vertebral artery occlusions or occlusion of a unilateral vertebral artery that is the sole supplier of the basilar artery, even in the presence of patent basilar artery, will be considered de facto BAO.)

(3) CT or MRI ruling out intracranial hemorrhage,

(4) Eligible for IVT and EVT (within 4.5 hours of symptom onset). (Symptoms onset is defined as point in time the patient was last seen well [at baseline] if patients are unable to provide a reliable history or the point in time when symptoms have started if patients can provide a reliable history. Symptoms onset includes diplopia, midline ataxia, visual loss, sensory or motor deficits, and conscious disturbance. Isolated vertigo [not accompanied by dysarthria, motor weakness, sensory symptoms, double vision, depressed level of consciousness] is not considered onset of symptoms.)

(5) NIHSS score ≥ 6 .

(6) Age ≥ 18 years.

(7) Signed informed consent by the patient or legal representative.

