6.4 Description and justification of route of administration and dosage

The route of administration and dosage are determined based on the 2019 AHA/ASA guidelines for early management of AIS.

7. Non-investigational products

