Neuroimaging to assess the site, severity, and patency of vascular lesions should be performed before or simultaneously with intravenous rtPA administration to save time and resources. The aim is to allow rtPA infusion before EVT without causing delays.

3. IVT agent, dosage, and route

If deemed necessary by the interventionalist, the use of local (intra-arterial) rtPA is permitted for all patients in this trial. Patients who have already received IVT should not be administered more than 30 mg of intra-arterial rtPA during the EVT procedure. The SC recommends that rtPA be given as a 5 mg bolus at a 5–10 min interval and that vascular patency be checked after each bolus.

For patients in the EVT alone group who do not achieve successful reperfusion (defined as eTICI 2b–3) within the 4.5-hour time window and do not achieve the maximum rtPA dose, they may subsequently receive IVT with rtPA at a dose of 0.9 mg/kg. The total amount of rtPA for IVT received before and after EVT should not exceed the dose specified in the guidelines.

4. EVT devices

This trial does not limit the choice of interventional techniques during EVT. NMPA-approved endovascular devices are all allowed to be used as the primary tools in this trial. Secondary devices may be utilized based on the interventionalist's discretion in cases of primary device failure. Further device selection for specific patients are also determined by the interventional specialist. Details of endovascular devices, including model, specifications, quantity, and usage sequence, as well as type of anesthesia and sedatives (if used), will also be recorded.

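### The rescue-IVT rule for EVT-alone patients ties the 4.5-hour limit to achieving reperfusion and sets no latest start time for the IVT itself

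*Protocol*

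**What the plan says.** Section 5.3 (Rescue medications) describes who may receive rescue thrombolysis: "For patients in the EVT alone group who do not achieve successful reperfusion (defined as eTICI 2b–3) within the 4.5-hour time window", and who have also not reached the maximum rtPA dose. Appendix 19, item 3, gives the same rule, with the permission worded as "they may subsequently receive IVT with rtPA at a dose of 0.9 mg/kg". In both places the limit that follows is on quantity: "The total amount of rtPA for IVT received before and after EVT should not exceed the dose specified in the guidelines". Neither place gives a latest time for starting the infusion.

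The 4.5-hour window for IVT appears as an enrolment criterion in section 4.3: "Eligible for IVT and EVT (within 4.5 hours of symptom onset". Section 5.1 states the general rule that the EVT-alone group does not receive IVT; 5.3 is a specific exception to it.

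The 2019 AHA/ASA guideline is cited in two relevant ways. The Protocol Summary introduces the interventions with "In accordance with the 2019 AHA/ASA guidelines for early management of AIS and recommendations from the steering committee (SC", and SAP 1.4 repeats this. Section 6.4 is more specific about what is taken from the guideline: "The route of administration and dosage are determined based on the 2019 AHA/ASA guidelines for early management of AIS". The SAP does not mention rescue IVT.

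**The concern.** The rule governs a full systemic dose of a thrombolytic given after an endovascular procedure. The same section permits intra-arterial rtPA for any patient, and section 5.2 calls for prompt clopidogrel or tirofiban after stenting. Intracranial haemorrhage and symptomatic intracranial haemorrhage are safety endpoints (8.1.3). The last time at which rescue IVT may start should therefore be written down.

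In the current sentence the time limit defines the failure (no eTICI 2b–3 by 4.5 hours), and the infusion comes afterwards. A site that follows the words may give IVT after the window. A site that assumes the usual IVT window still applies would not. Both could say that they followed the protocol.

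The trial comparison is also touched. Rescue IVT in the EVT-alone arm is part of what that arm receives, so uneven practice across sites makes the EVT-alone strategy less well defined.

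**Working it through.** The plan states no figure on this point, so the check is mainly textual.

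**Step 1. What the time limit modifies.** In 5.3 and Appendix 19 the 4.5 hours is attached to achieving eTICI 2b–3. The permission that follows carries dose conditions only: maximum rtPA dose not yet reached, 0.9 mg/kg, and a total within the guideline dose. The rule does not restate what the 4.5 hours is measured from; symptom onset is inferred from 4.3.

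**Step 2. Whether another section supplies a start time for rescue IVT.**

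| Section | What it covers | Rescue start time? |
|---|---|---|
| Protocol 4.3, criterion 4 | Eligibility at enrolment | No |
| Protocol Summary, Intervention; SAP 1.4 | General guideline reference | No |
| Protocol 5.2 | Guideline adherence for treatments other than IVT and EVT | No; IVT is excluded from the clause |
| Protocol 6.4 | Guideline basis for route and dosage | No |
| Protocol 12.4 | Treatments are approved and in line with current practice | No |
| SAP | No mention of rescue IVT | No |

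**Step 3. Whether late rescue can arise in ordinary cases (illustration only).** Let t be hours from onset to randomisation and d the hours from randomisation to groin puncture. Puncture falls after the window when t + d > 4.5, that is, when t > 4.5 − d.

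Inputs: 4.5 h from section 4.3. For d, section 5.1 gives a target median of 60 minutes or less for patients screened by CTA or MRA. It is assumed that randomisation can take place late in the 4.5-hour window.

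- d = 1.0 h (the target): 4.5 − 1.0 = 3.5 h. A patient randomised at 4.0 h is punctured at 4.0 + 1.0 = 5.0 h.
- d = 0.5 h (an assumed faster site): 4.5 − 0.5 = 4.0 h.

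A patient past the threshold cannot have eTICI 2b–3 from EVT by 4.5 h, so the time condition in 5.3 is met automatically. If EVT then fails, any IVT given after the attempt starts outside the window. Puncture comes before the failure is known, so rescue would start later than these times. Patients screened by DSA follow a different sequence and are not covered.

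**The case against.** The strongest reply is that the literal reading is strained. The sentence speaks of the 4.5-hour window as something already defined, and section 4.3 defines it for IVT eligibility. The heading is about rescue, the Summary places the interventions under the 2019 guideline, the Introduction describes the evidence for IVT as "within 4.5 hours of symptom onset in AIS have been confirmed by numerous randomized controlled trials", and section 12.4 says that treatments follow current practice. All of this makes the narrower intent likely, and that much stands. It does not answer the point: none of these sections states when rescue IVT must start, and the one section that says what is taken from the guideline names route and dosage only.

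Several stronger readings are tempting, and the documents do not support them.

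- A reader might infer that the two interpretations give sites opposite orders. They do not. The rule is permissive, so one reading allows late IVT and the other does not; neither requires it.
- A reader might infer that the rule licenses IVT in a patient who was reperfused shortly after 4.5 hours. The grammar allows it, but such a patient has no need of rescue.
- A reader might take the phrase "ultra-early treatment for AIS within 6 hours of onset" in the Introduction as a rival trial window. It is background narrative and sets no rule.
- A reader might treat 3.5 h as a firm cut-off or turn it into a share of patients. The 60 minutes is a target median stated as an upper value, so many patients may be faster. Section 4.2 also requires a median door-to-puncture time under 90 minutes, an interval that for direct admissions begins before randomisation.
- A reader might see a contradiction between 5.1 and 5.3. They are a general rule and its exception.

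In the other direction, a reader might conclude that the primary analysis is untouched because the m-ITT set is analysed by randomised group (SAP 3.1.2). That fixes how patients are classified. It does not stop rescue IVT in the EVT-alone arm from affecting outcomes, and hence the contrast.

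**Conclusion.** The point holds as a gap in a stated treatment rule. As worded, 5.3 and Appendix 19 permit rescue systemic rtPA to begin more than 4.5 hours after onset in EVT-alone patients whose reperfusion failed, and no other section sets a latest start. The sponsor probably intends a narrower rule, but the documents do not state it.

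No size is attached. The documents contain no rescue rate and no distribution of treatment times, so neither the number of patients affected nor any change in haemorrhage rates or in the treatment contrast can be estimated. The timing figures rest on the target in 5.1 and on an assumed 30-minute alternative; they show only that the situation can arise without unusual delay.

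Severity: minor safety clarification. Confidence is high on the wording; nothing is claimed about practical harm.

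**What to change.** In Protocol 5.3 and Appendix 19, item 3, replace the condition with: *Rescue IVT may be given only if eTICI 2b–3 has not been achieved with EVT and IVT can start within 4.5 hours of symptom onset.* Tell sites of the change. If later rescue is in fact intended, state the latest permitted start time instead.

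The cost is one sentence in two places and a site memo. IVT dose, route and administration time are already recorded (8.1.4), so no new data are needed and past use can be checked. The downside is that fewer late-presenting EVT-alone patients could receive rescue IVT.

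Two additions would be tidy but are optional: a cross-reference to 5.3 in section 5.1, and a line in the SAP saying how patients who had EVT and then rescue IVT are classed in the as-treated and safety sets.

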6.1 Name and description of the investigational products

The IVT drug used in this trial is rtPA (Alteplase), a thrombolytic agent composed of a glycoprotein with 526 amino acids. It binds to fibrin via lysine residues and activates fibrin-bound plasminogen, converting it into plasmin. Clinically, it is primarily indicated for the treatment of acute myocardial infarction, pulmonary embolism, acute ischemic stroke, deep vein thrombosis, and other vascular diseases.

6.2 Summary of clinical research findings

Currently, there are no RCTs comparing IVT followed by EVT with EVT alone in posterior circulation AIS patients. The IST-3 trial, which evaluated the efficacy of IVT in posterior circulation AIS, found that its benefits in this population were similar to those observed in anterior circulation AIS^[26]. A meta-analysis of 13 studies demonstrated that posterior circulation AIS patients treated with rtPA had better functional outcomes than those with anterior circulation AIS, while the risk of symptomatic intracranial hemorrhage was approximately half^[13]. These findings suggest that IVT with rtPA is similarly effective in posterior circulation AIS compared to anterior circulation AIS, with a lower bleeding risk.

6.3 Summary of known and potential risks and benefits

The known potential adverse effects of rtPA can be found in its product information leaflet.

6.4 Description and justification of route of administration and dosage

The route of administration and dosage are determined based on the 2019 AHA/ASA guidelines for early management of AIS.

7. Non-investigational products

7.1 Name and description of non-investigational products

In this trial, EVT procedures include retrievable stent thrombectomy, thrombus aspiration, balloon angioplasty, stent implantation, or combinations thereof (excluding DSA during the screening phase). The specific EVT approach for each patient will be determined by the treatment team based on the patient's condition. Endovascular devices approved by the NMPA will be used as the preferred devices during EVT.

7.2 Summary of other clinical research findings

To date, four RCTs have evaluated EVT for AIS-BAO. The first-generation thrombectomy trials, BEST and BASICS, failed to demonstrate the superiority of EVT^[9, 10]. However, more recent trials with improved designs and higher quality, such as ATTENTION and BAOCHE, confirmed that EVT significantly improves functional outcomes in AIS-BAO patients within 24 hours of symptom onset compared to standard treatment. These studies showed an approximately 22–23% increase in the proportion of patients achieving disability-free outcomes at 3 months. Standard treatment typically includes intravenous rtPA. Interestingly, a subgroup analysis of the ATTENTION trial suggested that patients who did not receive IVT might benefit more from EVT, leaving the efficacy and safety of IVT followed by EVT versus EVT alone in posterior circulation stroke unresolved.

7.3 Summary of known and potential risks and benefits

Potential risks include intracranial and extracranial hemorrhage, hemorrhagic transformation of the infarct, procedural risks such as dissection, perforation, and embolization in other vascular territories, as well as post-procedural risks such as infection. Previous studies on anterior circulation AIS indicated that the risk of hemorrhagic events and hemorrhagic transformation are comparable between IVT followed by EVT and EVT alone. Post-procedural complications, such as pneumonia and other infections, are similarly infrequent, and procedural complications are rare.

Both retrievable stent thrombectomy and thrombus aspiration, as primary EVT methods for AIS-BAO, are NMPA-approved for recanalization of occluded large intracranial vessels. Numerous studies have demonstrated that vascular recanalization significantly improves clinical outcomes in these patients. While EVT carries inherent risks, the ATTENTION and BAOCHE trials both have confirmed that EVT combined with standard medical therapy significantly increases the proportion of good functional outcomes at 90±14 days compared with standard medical therapy alone for AIS-BAO^[11, 12]. Thus, participation in this trial ensures that enrolled patients receive evidence-based treatment, with individual patients benefiting from either of the assigned treatment strategies. Additionally, this trial will improve understanding of both treatment strategies, ultimately benefiting the broader patient population. Retrievable stent thrombectomy and thrombus aspiration techniques have been in use for several years, and only cerebrovascular disease interventionalists who are well-trained and experienced are permitted to participate in this trial. Therefore, patients receiving EVT are not exposed to additional risks in this trial. The risks and benefits associated with the procedures are described below.

